### **8.7.2.3 Descriptive Analysis**

#### **8.7.2.3.1 Description of Study Enrollment**

To summarize the study population selection from the MID-NET database based on the study eligibility criteria, an attrition table will be provided. It will show the counts and percentages of excluded and remaining patients for each inclusion/exclusion criterion at every step of patient selection.

### 8.7.2.3.2 Description of Patient Characteristics

Patient demographic and clinical characteristics during the baseline period will be summarized and by treatment groups.

### 8.7.2.4 Analysis of the Primary, Secondary, and CCI

Primary endpoint is consistent with primary objective.

- Composite endpoint of hospitalized AMI, cerebral hemorrhage and cerebral infarction

Secondary endpoint is consistent with secondary objective.

- Composite endpoint of hospitalized AMI, cerebral hemorrhage and cerebral infarction

CCI

We will use two methods to estimate the incidence of each endpoint. First, we will calculate simple incidence rates (total number of patients with at least one event in the cohort divided by the sum of person-time to the first censoring event in the cohort) multiplied by 100 for each outcome and cohort. These rates do not account for treatment selection. Second, we will estimate propensity scores for each patient in the cohort using multivariable logistic regression with baseline covariates related to patient and clinical characteristics (see Section 8.3.3). The propensity score balances the distribution of observed covariates between treatment groups. We will include covariates that are either true confounders (to reduce bias) or related to the outcome (to increase precision). We will avoid covariates that are only related to the exposure but weakly related to the outcome, as they may decrease precision without reducing bias much (Brookhart et al, 2006). We will use inverse probability of treatment weights (IPTW) to estimate the rates of each outcome by time t in the overall patient population.

Specifically,  $F(T(a) < t)$  will be estimated with:

$$F(T(a) < t) = \frac{1}{n} \sum_{i=1}^n \frac{I(T_i < t) I(A_i = a) \Delta_i}{\Pr(\Delta_i = 1 | A_i, W_i)}$$

where  $A_i$  is an indicator of the observed treatment assignment,  $T(a)$  is the time of the (possibly counterfactual) outcome that would be observed if the patient were treated with  $A_i=a$ , and  $\Delta_i$  is an indicator that the patient was uncensored.

The propensity score model,  $\Pr(A_i=a|W_i)$ , will be estimated using logistic regression, and will contain a rich set of baseline covariates detailed in Section 8.3.3. We will estimate the hazard ratio and 95% confidence interval bands at 12 months by using COX proportional hazards model. Patients will be censored if any of the following happen: they discontinue the study medication (or switch to a different medication), one year from the start of study medication (index date), end of available data in the database, or death, whichever is earliest.

For the secondary, the same approach will be performed by the level of renal insufficiency.

Using the negative control outcomes, we will determine whether we still observe unmeasured confounding (ie, a non-null association between treatment groups and negative control outcomes) after adjusting for measured confounders. However, it is possible that our negative control outcomes do not account for all the different and relevant domains of unmeasured confounding and, therefore, we could have some bias in our assessment of residual confounding. Negative control outcomes will be identified with the help of the Japanese KOLs, in order to include the most relevant negative control outcomes for the Japanese population. Negative control outcomes will be assessed in the 1 year following index date. The potential negative control outcomes may include:

- Hospital for trauma or injury
- Dementia (fragility bias)
- Health-seeking behavior related to healthy-user bias (To be determined)

An NCO should be independent of the exposure, share the same confounders as the outcome of interest and be measurable and common enough in the target population to allow for effect estimation. The SAP will describe the criteria for selecting an NCO that reflect the confounding processes and how the rules are made that determine how to interpret NCO effect estimates.

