Three cohorts will be created mutually and defined based on the prescriptions received for:

- Romosozumab
- PTH analogs: teriparatide, abaloparatide
- Oral alendronate

- Covariates

- Patient and healthcare characteristic
- Fracture risk factors
- Cardiovascular risk factors
- Use of cardioprotective therapies
- Historical use of anti-osteoporosis drugs
- Level of renal insufficiency

- Study Sample Size

Using the MID-NET 2021 open data, we estimated the number of patients who received romosozumab, teriparatide, or oral alendronate over 5.5 years. The expected sample size for this study is: 3,850 patients for romosozumab, 8,500 patients for teriparatide, and 60,000 patients for oral alendronate.

- Data Analysis

- Summary Statistics:

Patient demographic and clinical characteristics will be summarized by cohort of exposure. Discrete variables will be summarized using frequencies and proportions, and continuous variables will be summarized using means and standard deviation (SD) or median and interquartile range (IQR). Incidence rate (number of events divided by person-time of follow-up) of the various outcomes in each exposure cohort will be estimated along with 95% confidence intervals (CI) as a measure of precision.

- Approach to primary objective:

Propensity scores will be calculated for each patient using multiple logistic regression modelling based on baseline demographic characteristics and clinical characteristics. Inverse probability of treatment weights (IPTW) will be created using propensity scores to minimize the measured confounding in the comparison of patients initiating romosozumab relative to patients initiating other specific osteoporosis therapies. Standardized mean differences (SMD) will be used to assess the differences in baseline patient characteristics between the treatment groups. Negative control outcome analyses will be used to detect presence of unmeasured confounding. COX proportional hazards model in the weighted sample will be used to estimate hazard ratio.

- Approach to secondary objective:

The same approach will be performed by the level of renal insufficiency:

1) no chronic renal disease (or eGFR  $\geq 90$  mL/min/1.73 m^2), 2) stage I or II Chronic Kidney Disease (CKD) (or eGFR 60-89 mL/min/1.73 m^2), 3) stage III CKD (or eGFR 30-59 mL/min/1.73 m^2), or 4) stage IV or V (or eGFR  $< 30$  mL/min/1.73 m^2).

- Bias analysis:

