#### **8.7.1.2 Primary Analysis**

To describe the study population, we will compute summary statistics for patient demographics and clinical characteristics as of the index date, stratified by the index treatment. Discrete variables will be summarized using frequencies and proportions, and continuous variables will be summarized using means and standard deviation (SD) or medians and interquartile range (IQR), as appropriate. For this study, propensity scores will be estimated and used to create IPTW for each patient in each pairwise treatment comparison. We will then assess the comparability of the weighted cohorts in each comparison, estimate the hazard ratio for each comparison and perform additional analyses to support the result interpretation.

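### The printed estimator for the adjusted risks omits the propensity score and leaves the censoring indicator undefined in time, so it returns crude risk times cohort share; the primary hazard ratio is not affected

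*Protocol*

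**What the plan says.** Protocol Section 8.7.2.4 gives two ways to estimate incidence. The first is the simple rate, of which it says "These rates do not account for treatment selection". The second is meant to supply that adjustment: "We will use inverse probability of treatment weights (IPTW) to estimate the rates of each outcome by time t in the overall patient population".

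The formula is introduced as the specific form of this second method. It is a sum over all n patients, multiplied by 1/n. In the extracted text the summand has the numerator and denominator "I(T_i < t) I(A_i = a) \Delta_i}{\Pr(\Delta_i = 1 | A_i, W_i". The denominator is therefore the probability of being uncensored and nothing else.

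The indicator Delta "is an indicator that the patient was uncensored"; no time point is attached. The propensity score model Pr(A=a|W) appears only after the formula, where it "will be estimated using logistic regression, and will contain a rich set of baseline covariates detailed in Section 8.3.3". The same section ends its list of censoring reasons with "one year from the start of study medication (index date), end of available data in the database, or death, whichever is earliest".

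The hazard ratio is specified separately. Section 8.7.1.2 says "propensity scores will be estimated and used to create IPTW for each patient in each pairwise treatment comparison", and the Abstract (Section 4) says "COX proportional hazards model in the weighted sample will be used to estimate hazard ratio".

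**The concern.** Inverse probability of treatment weighting divides each patient's contribution by the probability of the treatment received. Without that factor, an average over all n patients counts everyone in the other arm as a zero, so each arm's risk shrinks in proportion to its share of the pooled pair. Covariates W enter only through the censoring probability. That can address dependent censoring but not selection into treatment.

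This is the only confounding-adjusted risk estimator the protocol prints. Section 8.7.2.4 extends the same approach to the renal strata, and Section 10.2 says the safety outcomes will be reported as incidence rates. Section 8.7.2.1 also plans risk differences and risk ratios for negative control outcomes without naming an estimator. If this formula were used for them, the ratios would be non-null by construction, and Section 8.7.2.1 would read that as uncontrolled confounding.

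A second defect is that Delta has no time index while the one-year limit is itself listed as a censoring reason. It is therefore unclear whether a patient who completes one year event-free is censored or not.

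**Working it through.** **Inputs.** Cohort sizes are from Section 8.5: 3,850 romosozumab, 8,500 PTH analogs, 60,000 oral alendronate. Incidence (0.004 or 0.01 per person-year) and mean follow-up (0.6 or 0.8 years) are from Section 8.5 and Table 4. The protocol states no weighted risk and no discontinuation rate.

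**Plan's own figures.** 700 x 5.5 = 3,850, as stated. 1,551 x 5.5 = 8,530.5, close to the stated 8,500. The 60,000 is taken as given.

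**Step 1: what the formula estimates.** Leaving censoring aside, its expectation is

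E[I(T<t) I(A=a)] = Pr(A=a) x F(t | A=a),

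the cohort share times the crude arm risk. Weighting is pairwise, so the shares are:

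- vs PTH analogs: 3,850/12,350 = 0.312 and 8,500/12,350 = 0.688
- vs alendronate: 3,850/63,850 = 0.060 and 60,000/63,850 = 0.940

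**Step 2: equal true risks of 1%, no confounding.**

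| Pair | Romosozumab | Comparator | Ratio (truth 1.00) |
|---|---|---|---|
| vs PTH analogs | 0.312 x 1% = 0.31% | 0.688 x 1% = 0.69% | 3,850/8,500 = 0.45 |
| vs alendronate | 0.060 x 1% = 0.06% | 0.940 x 1% = 0.94% | 3,850/60,000 = 0.06 |

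The romosozumab risk is understated by a factor of 12,350/3,850 = 3.2 in the first pair and 63,850/3,850 = 16.6 in the second. The ratios do not depend on the incidence.

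**Step 3: confounding is left in.** A simulation of 4 million patients per pair assumed no drug effect, 30% high-risk patients (event hazard 0.025 vs 0.0036 per year) and an odds ratio of 0.4 for high-risk patients receiving romosozumab. Without censoring, the crude arm-risk ratio was 0.68 (PTH analogs) and 0.65 (alendronate). The printed formula gave 0.31 and 0.04: the confounding remains and the share scaling is added.

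Censoring was then added, with the propensity score in the denominator and the censoring survival evaluated at the event time. The risks were 0.00996/0.00996 for PTH analogs (ratio 1.00) and 0.0095/0.0100 for alendronate (ratio 0.96; simulation noise from the 6% arm). The true value is 0.0099 in both arms.

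**Step 4: the censoring term, under two readings of Delta.**

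*Reading A: Delta = 1 if the event occurs, or one year is reached, before discontinuation.* With rare events and a constant discontinuation hazard h, the share of events observed is (1 - exp(-h))/h, while Pr(Delta=1) is about exp(-h). Their ratio is the inflation.

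- 40% discontinue: h = -ln 0.6; 0.4/0.511 = 0.783; 0.783/0.6 = 1.31, about 30% too high.
- Mean follow-up 0.8 years: h = 0.464, exp(-h) = 0.629; 0.8/0.629 = 1.27.
- Mean follow-up 0.6 years: h = 1.126, exp(-h) = 0.324; 0.6/0.324 = 1.85.
- The simulation (h = 0.9, mean follow-up 0.66 years), with the propensity score included: 0.016 vs a true 0.0099, about 60% too high.

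*Reading B: Delta = 1 only if the event is observed, because reaching one year is listed as censoring.* At 12 months the numerator's expectation equals the denominator within each A and W. The formula then returns the cohort share itself (0.31/0.69 or 0.06/0.94), or 1.0 with the propensity score included. A usable risk estimate cannot come from this reading.

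**The case against.** The strongest objection is that the study's inference is a hazard ratio with its 95% interval (Section 6.6), and that ratio comes from a Cox model in the weighted sample, not from this formula. That stands. A reader might infer that the primary comparison is corrupted; the documents do not support it.

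The intent is also clear: IPTW is named before the formula and the propensity score model after it, so this looks like one dropped factor. A reader might infer that the sponsor chose not to adjust, or chose a formula that favours romosozumab. Nothing in the text supports either. But clear intent does not correct an estimator that is introduced as the specific one to use.

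The ratios 0.45 and 0.06 are not planned outputs for the cardiovascular endpoints, since the planned contrast there is the hazard ratio. That is right: they show the size of the distortion, not a result the study will report. A figure of this kind would also look odd beside the crude rates and might be caught.

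Loss of a factor in reading the PDF cannot be wholly excluded, but the fraction reads as complete.

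On censoring, the missing time index may be terse notation, and details of a censoring model are commonly left to the SAP. The discontinuation rates used above are assumptions. This part stands as a need to define Delta; a reader should not take 30%, or any other single figure, as the established bias.

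**Conclusion.** The formula in Section 8.7.2.4 is wrong as written and contradicts the sentence that introduces it. The missing propensity score is the certain, main defect. It scales each adjusted risk by cohort share (0.312 against PTH analogs, 0.060 against alendronate, at the planned sizes) and removes all adjustment for treatment selection. These shares rest only on the Section 8.5 cohort sizes; shares within renal strata are unknown, but the mechanism is the same.

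The censoring term is a secondary defect. Delta is not well defined, and a single whole-follow-up probability would overstate risk. Under a constant hazard with one-year completers counted as uncensored, the overstatement runs from about 27% to 85% across Table 4's two follow-up times. The actual size cannot be determined from the protocol.

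The error reaches the adjusted incidence estimates, overall and by renal stratum. It reaches the negative control contrasts only if they are computed with this formula. It does not undermine the primary hazard ratio. It should be corrected before the SAP is final.

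**What to change.** In Section 8.7.2.4, and in the SAP where it carries the formula, use

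F(T(a) < t) = (1/n) x sum over i of I(T_i < t) I(A_i = a) Delta_i / [ Pr(A_i = a | W_i) x Pr(C_i >= T_i | A_i, W_i) ],

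with the censoring survival evaluated at the event time T_i. Define Delta_i as the event being observed before discontinuation, end of data or other censoring, and state that the administrative end at one year does not count as censoring for t up to 12 months. Name the estimator to be used for the negative control risk ratios and differences. Normalising by the sum of the weights is optional.

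The cost is one formula and one definition. No new data are needed. Appendix C plans SAP completion for December 2025 and the start of analysis for January 2026, so the correction belongs before the first of these.

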#### **8.7.2.5 Sensitivity Analysis**

##### **8.7.2.5.1 Subgroup Analysis**

N/A

##### **8.7.2.5.2 Stratified Analysis**

N/A

##### **8.7.2.5.3 Sensitivity Analysis for Residual Confounding and Bias**

We will apply quantitative bias analyses to assess the extent of unmeasured confounding. We will explore one or more of the following methods. The rule-out method has been described previously (Schneeweiss S, 2006), is publicly available (Division of Pharmacoepidemiology and Pharmacoeconomics [DoPE], 2020) and has been applied extensively in the literature (Weintraub WS et al, 2012). An alternative method of evaluating unmeasured confounding involves assessing the strength of the measured confounders by removing each confounder individually from the model to develop a distribution of the point estimate of the hazard ratios to display the strength of the measured confounding. Assuming the unmeasured confounders fall within this distribution, the distribution can be used to inform the potential magnitude and direction of the unmeasured confounders on the validity of the effect estimate. Ding proposed a sensitivity analysis without imposing any assumptions on the unmeasured confounders. (Ding and VanderWeele, 2016). This quantitative bias analysis assesses the impact of unmeasured confounding at a range of confounding magnitudes. Another approach, the E-value provides the minimum strength of association on the RR scale that an unmeasured confounder would need to have with both the treatment and the outcome to move the treatment-outcome association to a specified level, conditional on measured covariates (VanderWeele and Ding, 2017). Upper bounds on the bias will be estimated and E-values will be calculated for the assessment of magnitude of bias due to unmeasured confounding.

##### **8.7.2.5.4 Other Sensitivity Analysis**

If the treatment effect varies with the propensity score, different methods will yield different result. Our primary analysis employs IPTW, which aims to balance the distribution of confounding variables between treated and untreated groups while closely approximating the overall study population. Additionally, we will conduct a sensitivity analysis using standard mortality ratio weighting (SMRW) to preserve the results of one of treatment arms (Brookhart M et al., 2013; Stürmer T et al., 2014). Considering the precautionary use of romosozumab as indicated in the labeling, it is possible that some

patients may have unmeasured contraindication for romosozumab. By applying SMRW to make the romosozumab group resemble the comparator group, we can estimate the average treatment effect in the population that was not affected by the warning.

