Romosozumab may potentially cause or worsen vascular calcification, but pre-clinical data indicate no impact on cardiovascular events (Amgen, 2019b). However, in an international, randomized trial of postmenopausal women with osteoporosis at high risk of fracture, romosozumab was associated with more serious cardiovascular events (2.5% versus 1.9%) than alendronate in the first 12 months (Saag et al, 2017). This trial did not include Japanese patients, unlike the FRAME study, which showed no difference (1.3% versus 1.3%) between the two treatments (Amgen, 2019b; Cosman et al, 2016). In September 2019, the Japanese package insert for romosozumab was updated in response to adverse drug reports following its launch. The revision included safety precautions related to cardiovascular events, as advised by Ministry of Health, Labor, and Welfare (MHLW) and Pharmaceuticals and Medical Devices Agency (PMDA) (PMDA, 2019).

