#### **6.4 Rationale**

As part of the Japanese Risk Management Plan for romosozumab, Amgen committed to conduct a post-marketing study to evaluate the risk of cardiovascular events in real-world users of romosozumab and those with renal dysfunction. As renal dysfunction is

associated with higher risk of cardiovascular events (Jankowski et al, 2021) and vascular calcification, especially in people on dialysis (Amgen, 2019b), this study will examine the risk of the cardiovascular events by the level of renal insufficiency. The overall approach of the proposed study, including study design, the data source, endpoints, comparator group, and overall analytic approach was previously agreed upon with the agency during the consultation meeting held on January 17, 2024.

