#### **8.7.1.3 Secondary Analysis**

For secondary objective, we will use the same method that we used in primary analysis and restrict to a subset that have available information on renal insufficiency. Since romosozumab and oral alendronate have a warning for use in patients with creatinine clearance less than 30 mL/min/1.73 m^2, patients treated with these therapies may exhibit a lower prevalence of renal insufficiency compared to those treated with PTH analogs. To ensure the comparability between treatment groups, we will limit the analyses to patients with similar levels of renal function to mitigate potential bias. The subgroup analyses will be performed based on the following criteria: 1) no chronic renal disease (or eGFR  $\geq$  90 mL/min/1.73 m^2), 2) stage 1 or II CKD (or eGFR 60-89 mL/min/1.73 m^2), 3) stage III CKD (or eGFR 30-59 mL/min/1.73 m^2), or 4) stage IV or V (or eGFR < 30 mL/min/1.73 m^2).

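### The SMRW sensitivity analysis targets comparator-treated patients, yet the protocol says it targets patients unaffected by the romosozumab warning

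*Protocol*

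**What the plan says.** Protocol section 8.7.2.5.4 describes the primary IPTW analysis as balancing confounders "while closely approximating the overall study population". It adds a sensitivity analysis "using standard mortality ratio weighting (SMRW) to preserve the results of one of treatment arms". The section opens with the point that methods differ when the effect varies with the propensity score. It then gives a specific reason for the chosen direction: because of the labelling, some "patients may have unmeasured contraindication for romosozumab". The direction follows: "By applying SMRW to make the romosozumab group resemble the comparator group, we can estimate the average treatment effect". The claimed target is the effect "in the population that was not affected by the warning".

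Three other places bear on this:
- Section 6.3, on the September 2019 change to the Japanese package insert: "The revision included safety precautions related to cardiovascular events".
- Section 8.7.1.3, on the renal warning shared by romosozumab and oral alendronate: "patients treated with these therapies may exhibit a lower prevalence of renal insufficiency compared to those treated with PTH analogs".
- Section 8.5, which expects 3,850 romosozumab, 8,500 PTH analog and 60,000 oral alendronate users.

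**The concern.** A warning on romosozumab moves some patients away from romosozumab. Those who remain in the study do so as comparator patients. The protocol makes the comparator cohort the standard population and calls it the one the warning did not affect. The group already screened by the warning is the romosozumab cohort. Section 8.7.1.3 applies that same logic to the renal warning: the arm carrying a warning is depleted of the patients it concerns.

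What is at stake is how the sensitivity result is read. If it agrees with the primary analysis, the wording invites the conclusion that channelling has been dealt with. The comparison gives no such assurance, and in the alendronate contrast the agreement comes close to being built in. Diverted high-risk patients left in the comparator arm make romosozumab look safer, which is the unfavourable direction of error in a safety study.

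**Working it through.** The protocol gives no figure for this analysis, so there is none to reproduce. The check covers the weights, the cohort shares and an illustrative calculation.

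**1. Weights implied by the text.** Let PS be the probability of romosozumab given measured covariates.

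| Analysis | Romosozumab weight | Comparator weight | Target population |
|---|---|---|---|
| IPTW (primary) | 1/PS | 1/(1-PS) | Whole pairwise pool |
| SMRW as written | (1-PS)/PS | 1 | Comparator-treated |
| SMRW reversed | 1 | PS/(1-PS) | Romosozumab-treated |

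Under the written version every diverted patient in the comparator cohort keeps weight 1 and helps define the target.

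**2. Overlap with the primary analysis.** Comparator shares from section 8.5:
- alendronate: 60,000/(3,850 + 60,000) = 94.0%
- PTH analogs: 8,500/(3,850 + 8,500) = 68.8%

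Since 1/PS = 1 + (1-PS)/PS, the romosozumab weights differ by exactly 1. At the average PS of 3,850/63,850 = 0.060 in the alendronate contrast they are 16.6 (IPTW) and 15.6 (SMRW as written). The comparator weights are 1.06 and 1. The two analyses are almost the same.

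**3. Illustrative calculation.** All inputs here are assumptions, not protocol values: a measured risk factor X (prevalence 30%, outcome ratio 2); an unmeasured contraindication U (outcome ratio 3); a true romosozumab ratio of 1.0; PS based on X only. In case (a), U has prevalence 3% if X=0 and 30% if X=1. The chance of romosozumab without U is 0.38 (X=0) or 0.20 (X=1), and U multiplies it by 0.1.

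- PS: X=0, 0.97×0.38 + 0.03×0.038 = 0.370; X=1, 0.70×0.20 + 0.30×0.02 = 0.146.
- Prevalence of U in romosozumab patients: 0.00114/0.3697 = 0.3% and 0.006/0.146 = 4.1%.
- Prevalence of U in comparator patients: 0.03×0.962/0.6303 = 4.6% and 0.30×0.98/0.854 = 34.4%.
- Mean risk relative to baseline, romosozumab: 1 + 2×0.0031 = 1.006 and 2×(1 + 2×0.0411) = 2.164.
- Mean risk relative to baseline, comparator: 1 + 2×0.0458 = 1.092 and 2×(1 + 2×0.3443) = 3.377.

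The within-stratum ratios are already biased: 1.006/1.092 = 0.92 and 2.164/3.377 = 0.64. The three weightings differ only in the share of X=1 over which they average:
- IPTW, share 30%: (0.7×1.006 + 0.3×2.164)/(0.7×1.092 + 0.3×3.377) = 0.762.
- As written, share 0.3×0.854/(0.7×0.6303 + 0.3×0.854) = 36.7%: ratio 0.741.
- Reversed, share 0.3×0.146/(0.7×0.3697 + 0.3×0.146) = 14.5%: ratio 0.825.

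The same formulae in four cases:

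| Case | U prevalence, X=0 / X=1 | P(romosozumab) without U, X=0 / X=1 | Factor for U | IPTW | As written | Reversed |
|---|---|---|---|---|---|---|
| (a) U tracks X, PTH-like | 3% / 30% | 0.38 / 0.20 | 0.1 | 0.762 | 0.741 | 0.825 |
| (b) U tracks X strongly, excludes romosozumab | 1% / 50% | 0.38 / 0.20 | 0 | 0.654 | 0.614 | 0.811 |
| (c) U tracks X, alendronate-like | 3% / 30% | 0.07 / 0.04 | 0.1 | 0.790 | 0.787 | 0.847 |
| (d) U independent of X | 10% / 10% | 0.38 / 0.20 | 0.1 | 0.805 | 0.807 | 0.800 |

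No column reaches 1.0. The written direction is further from 1.0 than IPTW in (a) and (b), and within 0.003 of it in (c) and (d). Reversal helps in (a) to (c) and is marginally worse in (d).

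**The case against.** Several points on the other side stand.

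- **Purpose.** The section opens with effect heterogeneity, and unmeasured confounding is assigned to the negative control outcomes (8.7.2.4) and quantitative bias analyses (8.7.2.5.3). A reader might infer that SMRW was added to remove channelling bias and fails at it. The text does not go that far, and no weighting on measured covariates could do so in either direction.
- **Remedy.** A reader might infer that reversing the weights cures the bias. It does not. In a simulation with a 10% contraindication that triples risk and is never given romosozumab, independent of measured risk, at the PTH share and a treatment log-odds slope of -1.0 per SD of measured risk, reversal moved the ratio from 0.79 to 0.75.
- **Size.** The protocol speaks of precautions as well as contraindication. If the warning halves romosozumab use instead of abolishing it (correlation with measured risk 0.5, an assumption), the simulated ratios are 0.91 as written against 0.92-0.95 reversed for alendronate, and 0.88 against 0.90-0.92 for PTH. The gain is at most about 0.04.
- **Weight instability.** For alendronate the effective romosozumab sample fell to 29% as written, but already to 31% under IPTW (never-treated case correlated with measured risk, slope -1.0). That loss belongs mainly to the primary analysis.
- **Romosozumab users.** Section 6.4 commits the sponsor "to evaluate the risk of cardiovascular events in real-world users of romosozumab". One might infer that no planned analysis addresses them. Incidence rates with intervals are planned for the romosozumab cohort; what is absent is a comparative effect standardised to it. An overall-population effect is also a legitimate choice.
- **Which warning.** Section 8.7.2.5.4 does not name it. Under the renal warning, which alendronate shares, patients would not simply be diverted to alendronate.

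One could also read the target as users of drugs without the warning. That does not rescue the sentence, because those cohorts include the diverted patients.

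**Conclusion.** The contradiction between weighting direction and stated target holds on the protocol's text alone and needs no simulation. The near-duplication of the primary analysis in the alendronate contrast follows from the 94% comparator share in section 8.5.

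The numerical consequence is uncertain. It depends on how common the contraindication is, how strongly it raises risk, how far it reduces romosozumab use and how well measured covariates predict it. The documents give none of these, so the figures above show direction and do not predict results in MID-NET. Where the contraindication tracks measured risk and largely excludes romosozumab, reversal moved the ratio appreciably towards the true 1.0 (0.77 to 0.89 for alendronate and 0.72 to 0.83 for PTH in the simulation at slope -1.0). Otherwise the change is small or slightly adverse.

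This should be fixed. It concerns one sensitivity analysis and how that analysis will be interpreted; the primary hazard ratio, cohorts and endpoint are unchanged.

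**What to change.** - Standardise to the romosozumab population: romosozumab weight 1, comparator weight PS/(1-PS). Name the estimand as the effect in patients who received romosozumab, and rewrite the last sentence of section 8.7.2.5.4 to match.
- If the comparator-standardised version is kept, label it the effect in comparator-treated patients and delete the claim "in the population that was not affected by the warning".
- State that neither direction removes an unmeasured contraindication, that reversal helps only as far as measured covariates predict it and can be slightly worse if they do not, and that residual bias is left to the negative control outcomes and quantitative bias analyses.
- Do not present agreement between IPTW and the comparator-standardised SMRW in the alendronate contrast as evidence against channelling.

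The cost is a few sentences and one weight formula, with no new data. Appendix C places SAP completion in December 2025 and the start of analysis in January 2026; the change should be made before any results are seen.
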